2.1 PROTOCOL SYNOPSIS

The Protocol Synopsis is in [Appendix 1](#). For additional details, see the Schedule of Assessments in [Appendix 2](#), [Appendix 3](#), [Appendix 4](#), and [Appendix 5](#).

2.2 OUTCOME MEASURES

2.2.1 Primary Efficacy Outcome Measures

The primary efficacy outcome measure for this study is the annualized rate of decrease in percentage of predicted FVC over 52 weeks (% FVC/year). See protocol for description of spirometry.

2.2.2 Secondary Efficacy Outcome Measures

The secondary efficacy outcome measures of this study are as follows:

- Annualized rate of decrease in 6-Minute Walk Test (6MWT) distance over 52 weeks
- Time from randomization to first occurrence of a $\geq 10\%$ absolute decrease in percentage of predicted FVC or death from any cause
- Annualized rate of decrease in percentage of predicted diffusion capacity of the lung for carbon monoxide (DL_{CO}) over 52 weeks
- PFS, defined as the time from study treatment randomization to the first occurrence of any of the following disease progression or death events:

Death from any cause

All-cause hospitalization

A decrease from baseline (relative change) of $\geq 10\%$ in FVC (L)

- Annualized rate of decrease in FVC (mL/year) over 52 weeks
- Annualized rate of change in A Tool to Assess Quality of Life in IPF (ATAQ-IPF) total score over 52 weeks (see protocol for description of the instrument)
- Time from randomization to first occurrence of St. George's Respiratory Questionnaire (SGRQ; see protocol for description of the questionnaire) worsening (total score) as defined by reaching Minimal Important Difference (MID; [Swigris et al. 2010](#))

Total Score ≥ 7 or death from any cause

- Time from randomization to non-elective hospitalization or death from any cause
- Time from randomization to first event of acute IPF exacerbation (defined below)

IPF exacerbation is defined as an event that meets all of the following criteria as determined by the investigator:

Unexplained worsening or development of dyspnea within the previous 30 days

And radiologic evidence of new bilateral ground-glass abnormality or consolidation, superimposed on a reticular or honeycomb background pattern, that is consistent with UIP

And absence of alternative causes, such as left heart failure, pulmonary embolism, pulmonary infection (on the basis of endotracheal aspirate or bronchoalveolar lavage if available, or investigator judgment), or other events leading to acute lung injury (e.g., sepsis, aspiration, trauma, reperfusion pulmonary edema)

- Time from randomization to death from any cause
- Time from randomization to Respiratory hospitalization
- Time from randomization to first occurrence of a $\geq 15\%$ absolute decrease in percentage of predicted DL_{CO} or death from any cause

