4.4.1 Type I Error Control Plan

The fixed-sequence testing procedure ([Westfall and Krishen, 2001](#)) will be used to control the overall type I error rate for statistical testing of the primary and key secondary efficacy endpoints.

Contingent upon statistical significance in the primary efficacy endpoint—annualized rate of decrease in percentage of predicted FVC over 52 weeks, the key secondary endpoints will be tested at a two-sided significance level of 5% in the order as shown below:

- Time from randomization to death from any cause
- Annualized rate of decrease in percentage of predicted DL_{CO} over 52 weeks
- Time from randomization to first respiratory-related hospitalization
- Time from randomization to first acute exacerbation or death from any cause
- Annualized rate of change in the ATAQ-IPF total score over 52 weeks
- Annualized rate of decrease in 6MWT distance over 52 weeks
- Time from randomization to first occurrence of a $\geq 15\%$ absolute decrease in percentage of predicted DL_{CO} or death from any cause
- Time from randomization to first occurrence of a $\geq 10\%$ absolute decrease in percentage of predicted FVC or death from any cause
- PFS defined as time to all-cause death, all-cause hospitalization or $\geq 10\%$ relative decrease in FVC (L), whichever occurs first

If a test is not significant at 0.05 level, then the subsequent test(s) will not be considered significant regardless of the associated p-value(s).

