4.4.3 Secondary Efficacy Endpoints

Time-to-Event Endpoints

The log rank test stratified by baseline lung function ($\text{FVC} < 50\%$ vs. 50% to 75% vs. $> 75\%$ predicted) will be used to compare the time to event endpoints between two treatment arms. The hazard ratio and its 95% CI will be estimated using a Cox regression model

stratified by baseline lung function. In fitting the Cox model, ties will be handled with the approximate likelihood method of Efron (1977). Kaplan-Meier plots will be provided.

Time-to-event will be measured in reference to the date of randomization. The primary efficacy assessments for the randomized placebo-controlled period are made on through the Week 52 visit, assessment on this day will be included for analyses of the randomized placebo-controlled period, but subsequent assessment during the open-label period or after Week 52 will be excluded. Patients are considered to be in the placebo controlled period even if they have discontinued study treatment if they would still be receiving placebo controlled study treatment had they not discontinued. For time to non-elective hospitalization or death from any cause, time to first event of acute IPF exacerbation, time from randomization to death from any cause, and time to respiratory hospitalization, patients not experiencing an event will be censored at the earlier of last known alive day, study day 368 or the last date during the placebo-controlled period.

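### Kaplan-Meier plots for time to respiratory hospitalization censor deaths and so modestly overstate the cumulative risk; cumulative incidence should be shown instead

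*Combined protocol and SAP*

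**What the plan says.** SAP 2.2.2 defines the endpoint as "Time from randomization to Respiratory hospitalization". SAP 4.4.1 lists it as "Time from randomization to first respiratory-related hospitalization", after all-cause death and the DLco slope. In that fixed sequence "the key secondary endpoints will be tested at a two-sided significance level of 5% in the order as shown below", so this endpoint is formally tested only if the primary, all-cause death and the DLco slope have all succeeded. It is the only time-to-event endpoint in the sequence that neither is death nor includes it.

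SAP 4.4.3 gives the analysis: "The log rank test stratified by baseline lung function", a Cox hazard ratio with the same stratification, and "Kaplan-Meier plots will be provided". For a group of endpoints that includes respiratory hospitalization, "patients not experiencing an event will be censored at the earlier of last known alive day, study day 368 or the last date" of the placebo-controlled period. The SAP does not spell out what happens to a patient who dies without a respiratory admission, but under this rule such a patient is censored. The separate rule in SAP 4.4.3 that counts deaths within 168 days of the last clinic assessment as events covers only the FVC, DLco, PFS and SGRQ endpoints.

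Acute IPF exacerbation is in the same position in SAP 2.2.2 and 4.4.3: no death component and the same censoring rule. The version in the SAP 4.4.1 sequence does include death. Neither document plans a cumulative incidence analysis for either endpoint.

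**The concern.** Death prevents a later admission. If deaths are censored, one minus Kaplan-Meier estimates how often patients would be hospitalized if nobody died, which is higher than the proportion who actually are. A patient who dies without an admission is handled like one whose follow-up simply ended.

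The sponsor's own reasoning suggests that the two events are related. The SAP amendment rationale added the endpoint because respiratory hospitalization predicts mortality, and Protocol 3.2.4 says that hospitalizations in IPF carry a poor prognosis. What is at stake is the absolute risk read off the plot, and the temptation to read the hazard ratio as an effect on that risk.

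**Working it through.** The documents give no event rate, power or expected result for this endpoint. SAP 2.3 covers only FVC, so there is no planned figure to reproduce here.

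**Inputs.** One-year mortality of 5.6% (GAP stage I) and 16.2% (stage II) is from SAP Appendix 6. It is used only as a range, since the trial's own mortality is not given. A one-year Kaplan-Meier hospitalization risk of 10% to 20% is an assumption. Hazards are taken as constant over the year, and every death is treated as occurring without a prior respiratory admission.

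**Formulas.** With hospitalization hazard h = −ln(1 − KM risk) and death hazard d = −ln(1 − mortality):
- one minus Kaplan-Meier = 1 − exp(−h)
- cumulative incidence = h/(h + d) × [1 − exp(−(h + d))]

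**Low end.** Mortality 5.6%, KM risk 10%: h = 0.1054, d = 0.0576. Cumulative incidence = 0.1054/0.1630 × (1 − 0.900 × 0.944) = 0.6464 × 0.1504 = 9.72%.

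**High end.** Mortality 16.2%, KM risk 20%: h = 0.2231, d = 0.1767. Cumulative incidence = 0.2231/0.3999 × (1 − 0.800 × 0.838) = 0.5580 × 0.3296 = 18.39%.

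| Mortality | 1 − KM | Cumulative incidence | Overstatement (points) | Relative |
|---|---|---|---|---|
| 5.6% | 10% | 9.72% | 0.28 | 2.9% |
| 5.6% | 20% | 19.46% | 0.54 | 2.8% |
| 16.2% | 10% | 9.18% | 0.82 | 8.9% |
| 16.2% | 20% | 18.39% | 1.61 | 8.7% |

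**If half the deaths follow an admission** (an assumption), only the other half compete. Mortality 2.8% with KM 10% gives 0.7877 × 0.1252 = 9.86%, an overstatement of 0.14 points. Mortality 8.1% with KM 20% gives 0.7254 × 0.2648 = 19.21%, an overstatement of 0.79 points.

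**Stage III.** At 39.2% mortality and KM 20%, cumulative incidence is 15.90%, an overstatement of 4.1 points. That would describe a group made up entirely of stage III patients, not the trial population.

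**Effect on the arm contrast when the mortality gate is just passed.** In Cohort B (330 patients, 1:1), mortality of 5.6% and 16.2% gives about 18.5 and 53.5 deaths. Two-sided significance at 0.05 then needs an observed death hazard ratio of about exp(−1.96 × 2/√deaths), that is 0.402 and 0.585. With identical hospitalization hazards in both arms the Kaplan-Meier curves coincide, but the cumulative incidences on placebo and lebrikizumab are:
- 9.61% and 9.84% (mortality 5.6%, KM 10%)
- 8.98% and 9.39% (mortality 16.2%, KM 10%)
- 18.0% and 18.8% (mortality 16.2%, KM 20%)

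The plot hides a difference of 0.2 to 0.8 points.

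**Test.** An unstratified log-rank test was simulated with 330 patients, no hospitalization effect and 6,000 runs per scenario. It rejected in 4.3% (death hazard ratio 1) and 4.9% (death hazard ratio 0.58) of runs when the two events were independent. With an assumed shared frailty of variance 2 to 5 and death hazard ratios of 0.40 to 0.58, it rejected in 4.8% to 6.3%, with the mean z shifted by 0.07 to 0.32 against lebrikizumab. The highest figure came from the scenario with 39.2% mortality.

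**The case against.** The strongest reply is that nothing inferential is wrong. A cause-specific hazard analysis with mortality reported separately is an accepted approach, the log-rank test holds its level, and the SAP plans a plot but no Week 52 risk estimate. That stands, and it limits the point to the display and the labelling.

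The size is also an upper figure. Protocol 3.2.4 notes that placebo-arm mortality in recent IPF trials is low and that most hospitalizations are respiratory and correlate with cause of death. Many deaths may therefore follow an admission and not compete at all. The bias acts on both arms, so their contrast moves less. This stands too.

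A reader might infer that deaths are nowhere shown beside this endpoint. They are: all-cause death is the first key secondary, with its own test, hazard ratio and plot, and SAP 2.2.2 also has non-elective hospitalization or death. That composite includes non-respiratory admissions, however, and neither analysis corrects the respiratory hospitalization curve.

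A reader might also take Protocol 3.2.4 as warning against this censoring. It does not. Its remark on informative bias concerns treatment-related deaths wrongly classed as unrelated and then censored, and it is an argument for all-cause over cause-specific mortality.

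Finally, excess deaths on lebrikizumab passing for a hospitalization benefit could not readily become a formal claim, because "If a test is not significant at 0.05 level, then the subsequent test(s) will not be considered significant" and all-cause death is tested earlier.

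**Conclusion.** The point holds as a minor one about presentation. The plan implicitly censors deaths for respiratory hospitalization and shows only Kaplan-Meier, which overstates the one-year cumulative risk. The overstatement is at most about 0.3 to 1.6 percentage points (about 3% to 9% relative) at GAP stage I to II mortality, and roughly half that if half the deaths follow an admission. These figures rest on an assumed hospitalization risk of 10% to 20%, constant hazards and GAP mortality standing in for the trial's own.

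The documents do not support going further and calling the test invalid or the type I error uncontrolled. The log-rank test and hazard ratio answer a legitimate question about the cause-specific hazard and should be read as such.

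**What to change.** - Keep the stratified log-rank test and its place in the sequence, and label the Cox hazard ratio cause-specific.
- State in SAP 4.4.3 that death without the event is a competing event.
- Replace the Kaplan-Meier plot with Aalen-Johansen cumulative incidence curves, for respiratory hospitalization and for the SAP 2.2.2 acute exacerbation endpoint without death.
- Add respiratory hospitalization or death from any cause as a supportive analysis outside the testing sequence.

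The cost is a procedure option for two plots, some wording and one extra table. Alpha, sample size and data collection do not change. SAP Section 1 says this version was being amended before Cohort B was unblinded, so for Cohort B the change could be prespecified in that amendment. Cohort A had already been unblinded, so there it would be a post hoc display.

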2.2.3 Exploratory Efficacy Outcome Measures

The exploratory outcome measures for this study are as follows:

- Change from baseline to Week 52 in radiographic findings on pulmonary high-resolution computed tomography (HRCT), including quantitative lung fibrosis (QLF) score (see protocol)
- Change from screening (corresponding to timing for randomization strata) in serum and plasma biomarkers (e.g., periostin and CCL18) and change from baseline in serum and plasma biomarkers (e.g., periostin, CCL18, YKL40, COMP, OPN, CCL13)
- Serum lebrikizumab concentrations during the extended treatment and the 14-week safety follow-up period
- Exposure-response relationships (to be evaluated as warranted)
- Change from baseline to Week 52 in the Borg CR10 Scale
- Change from baseline to Week 52 in the ATAQ-IPF

- Time from randomization to first occurrence of SGRQ individual domain worsening as defined by reaching MID ([Swigris et al. 2010](#)).
 - Symptom=8
 - Activity=5
 - Impact=7
 - or death from any cause
- Change from baseline to Week 52 in the SGRQ
- Annualized rate of decrease in oxygen saturation levels (SpO₂) (%) over 52 weeks

The analysis plan for the exploratory HRCT and biomarkers will be specified in a separate document.

2.2.4 Pharmacokinetic Efficacy Outcome Measures

The pharmacokinetic (PK) outcome measures for this study are as follows:

- Serum lebrikizumab concentration at Week 52 (C_{Wk52})
- Predose serum lebrikizumab concentrations (C_{min}) at Weeks 4, 12, 24, and 36 ($C_{min,Wk4}$, $C_{min,Wk12}$, $C_{min,Wk24}$, and $C_{min,Wk36}$)

2.2.5 Safety Outcome Measures

The safety outcome measures are the same as those specified in the Protocol Synopsis (see [Appendix 1](#)).

2.3 DETERMINATION OF SAMPLE SIZE

Cohort A

Approximately 150 patients were to be enrolled. A sample size of 75 patients in each treatment group would provide over 85% power to detect a mean change from baseline in percentage of predicted FVC at 52 weeks from 6.6% to 3.0% (a 3.6% absolute difference or 54% relative reduction) under the assumption that the common standard deviation is 7% (as reported in the placebo group in the PIPF-016 [ASCEND] trial of pirfenidone). Power was estimated with use of a two group t-test at a 0.05 two-sided significance level.

A sample size of 75 patients in each treatment group will provide approximately 80% power to detect a change in the annualized rate of decrease in percentage of predicted FVC over 52 weeks from 7.2% to 3.5% (a 3.7% absolute difference or 51% relative reduction) under the assumption that the common standard deviation is 8% (as reported in the placebo group in the ASCEND trial of pirfenidone). Power was estimated with use of a two group t-test at a 0.05 two-sided significance level.

Cohort B

Approximately 330 patients were to be enrolled. A sample size of 165 patients in each treatment group would provide over 85% power to detect a mean change from baseline

in percentage of predicted FVC at 52 weeks from 3.7% to 1.3% (a 2.4% absolute difference or 64% relative reduction) under the assumption that the common standard deviation is 7% (as reported in the pirfenidone group in the ASCEND trial of pirfenidone). Power was estimated with use of a two group t-test at a 0.05 two-sided significance level.

A sample size of 165 patients in each treatment group will provide approximately 80% power to detect a change in the annualized rate of decrease in percentage of predicted FVC over 52 weeks from 4.1% to 1.6% (a 2.5% absolute difference or 60% relative reduction) under the assumption that the common standard deviation is 8% (as reported in the pirfenidone group in the ASCEND trial of pirfenidone). Power was estimated with use of a two group t-test at a 0.05 two-sided significance level.

2.4 ANALYSIS TIMING

The primary analysis for Cohort A was performed after all patients enrolled in Cohort A had either completed the placebo-controlled treatment visit (Week 52) or discontinued early from the study. Treatment assignment was unblinded when all data through the Week 52 visit were in the database and the data were cleaned and verified. The independent Data Coordinating Center (iDCC) that prepares the safety analyses for independent Data Monitoring Committee (iDMC) review prepared the unblinding data of Cohort A for the Sponsor to ensure that the Cohort B was not inadvertently unblinded, when Cohort A was unblinded.

The primary analysis for Cohort B will be performed after all patients enrolled in Cohort B have either completed the placebo-controlled treatment visit (Week 52) or discontinued early from the study. Treatment assignment will be unblinded when all data through the Week 52 visit are in the database and the data have been cleaned and verified.

3. STUDY CONDUCT

3.1 RANDOMIZATION

Patients were randomized to the treatment arms through the interactive voice/Web-based response system (IxRS). After written informed consent is obtained, patients received a screening number, which was assigned by the IxRS. Following completion of the screening period and after all patient eligibility requirements were confirmed on Day 1, patients were to be assigned an identification number (a different number from the screening number) and randomized in a 1:1 ratio to one of two treatment arms for the 52-week placebo-controlled study period:

- **Cohort A** - lebrikizumab 250 mg SC or placebo SC every 4 weeks
- **Cohort B** - lebrikizumab 250 mg SC every 4 weeks and pirfenidone \leq 2403 mg/d or placebo SC every 4 weeks and pirfenidone \leq 2403 mg/d

Patients were to be randomized on the same day that treatment was to be initiated (Day 1/Visit 2).

Dynamic hierarchical randomization was performed centrally and stratified by the following factors:

- **Cohort A:** region (United States, Europe/Canada, other), lung function (FVC < 50%, 50% to 75%, > 75% predicted), and serum periostin concentration (< 50 ng/mL, ≥ 50 ng/mL)
- **Cohort B:** region (United States, Europe/Canada, other), lung function (FVC < 50%, 50% to 75%, > 75% predicted), and serum periostin concentration (< 50 ng/mL, ≥ 50 ng/mL). Although in the protocol amendment version 6 (2 December 2015) the region strata was to be replaced by prior perfenidone exposure but due to faster than anticipated accrual and logistic challenges this change was not implemented.

During the placebo-controlled study period and the open-label lebrikizumab treatment period, IxRS assigned study treatment kits for patients in Cohort A. During the placebo-controlled study period, IxRS will assign study treatment kits and pirfenidone treatment kits for patients in Cohort B. At each dosing visit during the placebo-controlled period, study and/or pirfenidone treatment kits will be distributed for administration. The placebo and active kits are filled and packaged to look identical. Patient randomization and treatment kit assignments will be verified on an ongoing basis by an external and independent statistical coordinating center to ensure that randomization and kit assignments are conducted correctly by IxRS.

The dynamic randomization scheme was employed with a biased-coin assignment whenever an imbalance at a given hierarchical level exceeds pre-specified thresholds. The dynamic randomization parameters (i.e., the allocation probabilities and the imbalance thresholds that lead to a biased-coin assignment at each level) will be provided in the Clinical Study Report (CSR).

Patients, all study site personnel, and the Sponsor and its agents (with the exception of the IxRS service provider, the external independent statistical coordinating center responsible for verifying patient randomization and study treatment kit assignments, PK/PD laboratory personnel, and the iDMC, iDCC, and IMC members) will be blinded to treatment assignment for each cohort until the unblinding for each primary analysis.

If unblinding is necessary for patient management (in the case of a serious adverse event [SAE]), the treatment code is available to the investigator through the IxRS. Treatment codes are not to be disclosed except in emergency situations. If the investigator wishes to know the study treatment assignment for any other reason, he or she is to contact the Medical Monitor directly. The investigator should document and provide an explanation for any premature unblinding (e.g., accidental unblinding or unblinding because of a SAE).

As per health authority reporting requirements, Roche will break the treatment code for all unexpected SAEs (see protocol) that are considered by the investigator to be related to study drug.

3.2 INDEPENDENT REVIEW FACILITY

See protocol for details on planned independent reviews for HRCT, surgical lung biopsy, and ECG.

3.3 DATA MONITORING

3.3.1 Independent Data Monitoring Committee

An independent Data Monitoring Committee (iDMC) will monitor safety and study conduct on an ongoing basis. Members of the iDMC will be external to the Sponsor, and will follow a charter that outlines the iDMC roles and responsibilities. The iDMC will meet approximately every 6 months to review unblinded safety and study conduct data provided by an iDCC. This will include a review of all deaths and hospitalizations reported on the adverse event (AE) forms. The study may be stopped early for safety reasons. If the iDMC determines that a benefit-risk assessment is necessary, the iDMC may also review unblinded efficacy data, although the iDMC may not recommend stopping the trial for positive efficacy. Full details of the meeting schedule and flow of information between iDCC and iDMC can be found in the iDMC charter.

